117 Hospital, and Abington Hospital.
- 118 c. Data analysis: *(Provide statistical design for primary endpoint only. Please*
119 *indicate how the study is powered and what statistical tool(s) will be applied.*
120 *Please do not cut and paste entire statistical section from the sponsor protocol.*
121 *Pilot studies do not require a statistical plan but need to outline how the results*
122 *will be used to power future studies.)*
123
- 124 • Sample size = 128 participants
125 80% power using 2-sided t test – would require 64 patients per group (128 total)
126 to show a 25% decrease in time to GI3 recovery in G-POCUS group vs standard
127 care group.
- 128 Sample size calculation was performed using a continuous variable as the primary
129 endpoint (number of days to GI-3 recovery), and assuming an alpha of 0.05 and a
130 power of 80%. Results from the pilot study were used to inform sample size
131 calculation. All patients in the pilot study took on average 1.5 days (SD 1-3 days)
132 to reach GI-3 recovery, while patients in the pilot study with empty stomachs on
133 G-POCUS on POD1, took 1 day on average (SD 1-2) to reach GI-3 recovery.
- 134 d. If the protocol involves sending tissue to a commercial entity, please certify that
135 the following criteria are met (see TJU policy #110.17, "Collection, storage, use
136 and distribution of tissue for research purposes"). Also, please provide a copy of
137 the sponsor contract/agreement or an e-mail from ORA certifying same. The PI
138 certifies that he or she (check applicable statements):

- Will have significant input into the study design and/or conduct of the study.
- Will receive experimental data and participate in data analysis.
- Has established the right to be a co-author on any publications related to this protocol.
- Certifies that Jefferson ORA is negotiating a sponsored research agreement, to be signed prior to work commencing.

5. Delineate procedures that are standard of care from those that are being performed specifically for the research. *Delete examples and add additional rows to table as appropriate. Provide the information to the best of your ability.*

Procedure	Research	Standard of Care
G-POCUS on POD1	X	
G-POCUS on POD 2-5, if criteria met	X	

6. Describe the Data and Safety Monitoring Plan (DSMP) for this protocol. See OHR Policy G 616 for guidance.

 X Study is minimal risk and does not require a DSMP. Accuracy of data will be confirmed by PI before study is locked.

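### The claimed 80% power for a 25% decrease in days to GI-3 recovery does not follow from the pilot figures cited: with the pilot mean as control mean and the smallest printed SD, 64 per arm gives 56%.

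*Protocol*

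**What the plan says.** Everything on this point is in Part A, item 4c (Data analysis) of the protocol.

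- Design claim: "80% power using 2-sided t test – would require 64 patients per group (128 total"), the target being "to show a 25% decrease in time to GI3 recovery in G-POCUS group vs standard" care.
- Endpoint and error rate: the calculation treats the primary "endpoint (number of days to GI-3 recovery), and assuming an alpha of 0.05 and a" power of 80%.
- Source of the planning values: "power of 80%. Results from the pilot study were used to inform sample size" calculation.
- Pilot, all patients: "All patients in the pilot study took on average 1.5 days (SD 1-3 days").
- Pilot, patients with an empty stomach: "G-POCUS on POD1, took 1 day on average (SD 1-2) to reach GI-3 recovery".

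No control-arm mean, absolute difference or single SD is named as the planning value.

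**The concern.** A two-sample t-test calculation needs a difference and one SD (or one per arm). The protocol gives a percentage decrease, two pilot means, and two ranges labelled as SDs. An SD is a single number, so the calculation cannot be repeated as printed. When the printed values are taken at face value, the claimed power is not reached.

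This is the trial's only power justification. If 64 per arm does not give 80% power for a 25% decrease, a null result could be read as evidence against a benefit that the trial had a substantial chance of missing. It is also unclear which difference the trial was sized to detect: 0.375 days, 0.5 days, or something else.

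This is not a detail that can wait for a statistical analysis plan. The form asks at this item how the study is powered, and the protocol answers with a specific figure. The question is whether that figure agrees with the inputs beside it.

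**Working it through.** **Inputs (all from item 4c).** Two-sided alpha 0.05; power 80%; 64 per arm, equal allocation; target decrease 25%; pilot mean 1.5 days (all patients) and 1 day (empty stomach); printed SD ranges 1-3 and 1-2 days.

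**Assumption.** The control mean is taken as 1.5 days. The protocol does not say so, but this is the only all-patient mean it gives.

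**Method.** The normal approximation is n per arm = 2 × (1.960 + 0.842)² × (SD/Δ)² = 15.70 × (SD/Δ)². The results below use the noncentral t, which usually adds about one patient per arm.

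**Step 1. What 64 per arm corresponds to.** For Δ/SD = 0.5, the approximation gives 15.70 / 0.25 = 62.8, so 63; the t calculation gives 63.8, so 64. Conversely, 64 per arm at 80% power detects a standardised difference of 0.499.

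**Step 2. Reproducing the plan's figure.** The pilot contrast is 1.5 − 1.0 = 0.5 days, which is 0.5/1.5 = 33%. With SD 1.0 this needs 64 per arm (power 80.1%). So 64 is reproduced exactly, but for a 33% decrease.

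**Step 3. The stated 25%.** 0.25 × 1.5 = 0.375 days. The SD needed for 80% power at 64 per arm is 0.375 / 0.499 = 0.75 days, below the smallest printed value of 1.0.

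**Step 4. The 25% target with the ranges read as SDs.**

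| SD in both arms | n per arm for 80% | Power at 64 per arm |
|---|---|---|
| 1.0 | 113 | 56% |
| 1.5 | 253 | 29% |
| 2.0 | 448 | 18% |
| 3.0 | 1006 | 11% |

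Testing one-sided does not restore the figure: at SD 1.0 it still needs 89 per arm.

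**Step 5. The 25% target with the ranges read as interquartile ranges** (an assumption; SD ≈ width/1.349, which presumes rough normality). The range 1-3 gives 2/1.349 = 1.48, and 1-2 gives 1/1.349 = 0.74. For unequal SDs, the root mean square is √((1.48² + 0.74²)/2) = 1.17.

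| SD control / G-POCUS | n per arm for 80% | Power at 64 per arm |
|---|---|---|
| 0.74 / 0.74 | 63 | 81% |
| 1.48 / 0.74 | 154 | 44% |
| 1.48 / 1.48 | 246 | 30% |

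**Step 6. A different control mean.** With SD 1.0, a 25% decrease is detectable at 64 per arm if 0.25 × mean = 0.499, that is, a mean of about 2.0 days. No such mean is printed.

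**The case against.** The best defence is that 64 per arm can be reached for a 25% decrease. If the range 1-2 is an interquartile range, the SD is about 0.74 and the calculation returns 63 per arm, with 81% power at 64. A control mean of about 2.0 days with SD 1.0 also works, and the pilot was in colorectal surgery whereas this trial admits colorectal or abdominal surgery, so its control mean could differ. Both points stand as possible explanations. Neither is stated in the protocol. The first also applies the spread of the empty-stomach subgroup to an unselected control arm, and the all-patient range read the same way gives 44% or 30%. A reader might therefore infer that 64 fits only a 33% decrease with SD 1.0; Steps 5 and 6 show that this goes too far.

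A reader might also infer that choosing 25% when the pilot contrast is 33% is itself a mistake. It is not. The protocol says that the pilot informed the calculation, not that the target equals the pilot contrast, and a target below an observational contrast can be a deliberate discount.

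Third, it is tempting to argue that the pilot contrast caps the achievable effect, so that a 0.5-day gain would mean removing all the excess delay of full-stomach patients. That assumes only those patients can benefit. Part A, item 1 says the algorithm also guides how diets are advanced, which could change recovery in empty-stomach patients too, and the algorithm figures in the Appendix are not shown. The documents do not establish such a cap. What does stand is that a comparison of all pilot patients with a subset defined by an examination finding is observational and does not estimate the effect of acting on that finding.

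**Conclusion.** The concern holds in this form: the statement of 80% power for a 25% decrease with 64 per arm does not follow from the pilot figures cited for it. With a control mean of 1.5 days and the most favourable SD printed, power is 56%, so a true 25% decrease would be missed about 44% of the time; larger SDs give less.

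The size depends on two things the protocol leaves open: the control mean, and whether the printed ranges are SDs or quartiles. The 18% and 11% figures at SD 2.0 and 3.0 follow from the printed labels. They should not be read as the likely power, since a range cannot be an SD and the labels are themselves doubtful. Under the quartile reading, power for 25% runs from about 30% to 81%, according to whose spread is used. The conclusion that the text needs correcting does not depend on which reading is right, because each one requires a change to what is printed.

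**What to change.** Rewrite the sample-size paragraph in item 4c from the pilot patient-level data:

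- Replace each range with a single SD. If the ranges are quartiles, label them so.
- State one control-arm mean, one absolute difference in days with its percentage, and one planning SD (or one per arm), and say which pilot group each comes from.
- Restate the power or the detectable effect for 64 per arm from those values. If the SD is 1.0, for example, the paragraph could claim 80% power for a 0.5-day (33%) decrease from 1.5 days, or keep the 25% target and give its power as 56%.
- Add a sentence that the pilot difference compares all patients with those who had an empty stomach, is observational, and does not estimate the treatment effect. Do not describe it as an upper bound.

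The cost is one paragraph and a short reanalysis of existing pilot data. The sample size can stay at 128. The drawback is that the stated power or detectable effect may look less favourable.

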JEFFERSON—Office of Human Research

SUMMARY OF INTERVENTIONAL HUMAN SUBJECTS RESEARCH

Version Date – FOR OHR USE: 11/11/21

Please address all applicable points to create a complete and succinct synopsis of the protocol. If a point does not apply to your study, please state “NA.” Use language, insofar as is possible, that can be understood by a layperson, and provide meanings for all acronyms used. Please maintain all questions in the body of the text. For non-interventional research (questionnaires, surveys, and all sociobehavioral research), use form OHR-2B. **Form must be typewritten.**

PART A - SUMMARY OF STUDY

1. Brief Summary

a. Provide a brief (2-3 sentences) lay language synopsis of the study. Include an explanatory sentence about the study article (*e.g., product X is a compound that increases excretion of salt and therefore may be of use in the treatment of high blood pressure*)

- Gastric point of care ultrasound (G-POCUS) can show if a postoperative patient’s stomach is empty or full, and a full stomach has been correlated with delayed return of bowel function after surgery, longer time to GI-3 recovery (defined as the ability to tolerate a regular diet and have either flatus or bowel movement), and increased length of stay. In the study group, patients will have a gastric POCUS exam at 0600 on post-operative day 1 and daily thereafter until they have return of bowel function whereas in the control group, patients will receive standard postoperative care without the addition of any G-POCUS exams. In the study group, the results of the G-POCUS exams will be employed in a care algorithm designed to help clinicians decide how to advance patients’ diets and when to place and remove nasogastric tubes (NGT).

2. Objectives and Significance

a. State the primary objective(s) of the study.

- Determine if using G-POCUS as a clinical decision-making tool reduces rates of aspiration pneumonia/pneumonitis, length of hospital stay, need for additional/unplanned procedures in the patient population.

b. State the secondary objectives(s) of the study.

- Secondary: Determine if G-POCUS can be used to develop clinical practice guidelines for when to advance/de-escalate diets postoperatively and when to insert/remove NGTs in patients who are recovering from abdominal/colorectal surgery.

c. What benefit or knowledge will be gained?

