75 incidence of DBF, length of stay, emesis, and need for NGT placement.
76

77 4. Briefly describe the research design. (*Use charts and flow diagrams if applicable.* “*See*
78 *protocol” is not an acceptable response.*)
79

80 a. Subjects: State inclusion and exclusion criteria.

81 • Inclusion criteria:

- 82 ○ Completed signed and dated informed consent form
- 83 ○ Willing to comply with all study procedures
- 84 ○ Male or female, 18 years of age or older
- 85 ○ Presenting for a schedule elective colorectal/abdominal surgery, either open
86 or laparoscopic

87 • Exclusion criteria:

- 88 ○ History of gastroparesis or known gastric/intestinal motility disorder
- 89 ○ History of gastric/bariatric surgery
- 90 ○ Intubated/sedated postoperatively
- 91 ○ Presence of open abdominal wounds (including abdominal wound vac)
- 92 ○ Patients who received a complex abdominal wall reconstruction
- 93 ○ Class III/IV Wound (Contaminated/Infected/Dirty)

- 94 ○ Surgery was emergent/urgent/unscheduled
95 ○ NGT placed or present at time of operation
96 ○ Presence of ileostomy/colostomy
97 ○ J-pouch reconstruction patients
98 ○ Currently pregnant patients
99 ○ Patients aged <18 years old
100
101 b. Procedures: Provide study visit details.
- 102 • This will be a randomized single-blinded study of handheld G-POCUS in which
103 our study population will be inpatients hospitalized after abdominal/colorectal
104 surgery at TJUH, Methodist Hospital, or Abington Hospital. Patients will be
105 randomized to an unblinded intervention arm or an unblinded standard of care
106 arm. On POD1, patients will be asked if they are having any GI symptoms. These
107 are defined as presence of nausea, emesis, belching, and/or hiccups. In the
108 intervention arm, clinicians will use the results of G-POCUS and
109 presence/absence of GI symptoms to inform decision making according to one of
110 two standardized algorithms (see Appendix). In the control arm, presence of GI
111 symptoms will be assessed, and once of two standardized algorithms which are
112 representative of the current standard of care for postoperative diet management.
113 Data from both groups will be used to determine if the G-POCUS studies' results
114 can predict the incidence of primary or secondary outcomes (control) or if
115 intervening on results of G-POCUS can decrease the incidence of undesirable
116 outcomes. This will be a multicenter study enrolling patients at TJUH, Methodist

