 329 requirements to a CRO and investigator will obtain an audit from a CRO to ensure that
 330 procedures are in place so that all other FDA regulatory requirements of sponsors will be
 331 met.

332
 333 NOTE: If you intend to use someone who is in-house and who has expertise on sponsor
 334 requirements, please justify that that person has equivalent expertise to a CRO.
 335

- 336 3. Identify all non-investigational medications and/or devices specified in the protocol that the
337 subject will receive while on this study. *This refers to drugs or devices that the subject will receive*
338 *but are not being tested as part of this study.*
339 • Gastric POCUS studies will be obtained using Kosmos, a handheld portable ultrasound
340 that is FDA approved for clinical use. This product has already been validated for use, and
341 this is not a novel application of the technology.
342

343 **II. Drugs**

344
345 **Does study involve drugs?** YES _____ NO X
346

347 **III. Devices**

348
349 **1. Does study involve a device?** YES ___ NO X If no, delete the REST of this Device
350 section.

351 *If YES, please submit OHR-25 Investigational Device Worksheet.*
352

353 **2. Does the study involve an in vitro diagnostic device?** YES _____ NO X
354

355 *If YES, please submit OHR-28 In Vitro Diagnostic Device Worksheet.*
356

357 **PART D - RISKS, BENEFITS, AND ALTERNATIVES**

358
359 **1. What are the risks of the research?**

- 360 • There are minimal risks involved in participation. The main risk is mild physical
361 discomfort during the ultrasound exam.
362

363 **2. Discuss how the study design minimizes risks and maximizes benefits associated with this study.**

- 364 • This study poses minimal risk to enrolled participants above what is standard of care at
365 Jefferson. If a patient at any point in time feels uncomfortable with the ultrasound, they
366 may request that the care team stops and they will be removed from the study immediately.
367

368 **3. What are the potential benefits of participation?**

- 369 • Benefits of participation include possible reduced risk of delayed bowel function and
370 postoperative ileus. Additionally, the information we learn during this study may help
371 patients in the future.
372

373 **4. Explain how the risks of the research are justified by potential benefit to the subject or society.**

- 374 • By implementing ultrasound into the patients' evaluation, there is minimal risk than

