375 standard of care. However, with this additional clinical information, a more informed
376 decision can be made regarding their bowel function and diet status, potentially leading to
377 increased clinical accuracy, and better patient outcomes.
378

379 **5. How would you treat this patient in a non-investigational setting? Please describe the treatment**
380 **that is considered standard of care, as well as any alternative procedures or drugs or other**
381 **courses of therapy that might be used, if such alternatives exist (include palliative care).**

- 382 • The current standard of care for assessing the risk for both of these complications heavily
383 relies on interview and physical exam, both of which can be skewed by subjective
384 differences amongst patients.
385
- 386 6. How do the risks and side effects of the standard therapies compare to those associated with the
387 study therapy?
- 388 • The side-effect of gastric ultrasound is mild discomfort during the examination. If a patient
389 experiences this, and wishes to terminate the exam, they will not receive additional gastric
390 ultrasounds and will be removed from the study.
391
- 392 7. If this is a placebo-controlled trial, please provide rationale for use of placebo.
393 • NA
394
- 395 8. If subjects will not receive standard of care, provide rationale for this and address risks of not
396 receiving standard of care.
397 • As stated in question 4, we are adding minimally-invasive diagnostic data into these
398 patients' care and, therefore, minimal risk is assumed by the patient. This will potentially
399 lead to more informed clinical decisions. This is a low-risk method by which we hope to
400 refine and redefine what the standard of care will be.
401
- 402 9. Please address any risks associated with a “washout” period if applicable.
403 N/A
404

PART E - CHILDREN

- 405
- 406
- 407 1. Will this study involve children (age 17 or under)?
408
- 409 ___ **YES** – Complete form OHR-26, “Research Involving Children” and submit as an
410 addendum to the OHR-2.
411 _**X**_ **NO** – Delete the REST of this Children section and skip to Part F.
412

PART F – RECRUITMENT, EQUITABLE SELECTION, AND CONSENT PROCESS

- 413
- 414
- 415 1. Discuss the recruitment plan and describe recruitment methods and materials (e.g., physician
416 referral, newspaper ad, radio, TV spot, e-mail, etc.).
417 • Patients will be recruited from our current clinical practice. No additional recruiting efforts

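### Stopping the ultrasound for discomfort means removal from the study, a rule only the intervention arm can trigger, so it allows one-sided loss after randomisation that can bias the comparison

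*Protocol*

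**What the plan says.** The rule is stated twice. Part D, item 2 says that a patient uncomfortable with the ultrasound "may request that the care team stops and they will be removed from the study immediately". Part D, item 6 covers a patient who wants an exam ended. The first half of its sentence stops the exams ("experiences this, and wishes to terminate the exam, they will not receive additional gastric"), and the second half adds the removal ("ultrasounds and will be removed from the study"). Removal is thus listed in addition to having no more exams, so the rule goes beyond ending the intervention.

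On who is examined, Part A, item 1a sets out the intervention schedule as follows: "patients will have a gastric POCUS exam at 0600 on post-operative day 1 and daily thereafter until they have return of bowel function". For the comparison arm, the same item states that "in the control group, patients will receive standard postoperative care without the addition of any G-POCUS exams". Part A, item 4b describes the allocation with the words "randomized to an unblinded intervention arm or an unblinded standard of care".

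One sentence in item 4b is unclear. It opens with "Data from both groups will be used to determine if the G-POCUS studies' results" and then speaks of predicting outcomes, with the word control in brackets. That could suggest exams in controls, but nothing in the protocol schedules any.

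Part A, item 7 takes patient data from Epic by chart review, along with a preoperative interview. A general right to discontinue, open to both arms, is stated separately in Part B, item 4 and Part F, item 16. Nothing in the protocol says whether outcomes of removed patients are kept.

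**The concern.** A randomised comparison is protected only while both arms keep the patients they were given. Here an event caused by the intervention itself takes patients out of one arm and has no counterpart in the other.

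The loss could be related to outcome in two ways:

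- **Clinical.** Patients who are distended, sore or nauseated may tolerate probe pressure less well and may also recover bowel function later. This is plausible, but the protocol does not state it.
- **Schedule.** Exams are repeated until bowel function returns, so a slow recoverer has more exams and more occasions to stop one. This applies even if discomfort has nothing to do with ileus.

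Both would remove slower patients from the intervention arm and make G-POCUS look better. Length of stay, aspiration and unplanned procedures, which Part A, item 2a names as primary objectives, are exposed in the same way. If aspiration is infrequent, one or two events lost from an arm of 64 could matter.

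**Working it through.** **1. The plan's own figure.** Part A, item 4c gives 64 per group, a two-sided t test, alpha 0.05 and 80% power. With standardised effect d, n per group = 2(1.960 + 0.842)²/d². For d = 0.5 this is 63 by the normal approximation and 64 by the t test, so the figure reproduces. The value d = 0.5 arises from 1.5 versus 1 day (0.5 day) with an assumed SD of 1.0, or from a 25% decrease (0.25 × 1.5 = 0.375 day) with an assumed SD of 0.75. The protocol gives SDs only as ranges, so both targets and both SDs are carried below. Enrolment is capped at 128 (Part B, item 1), with no allowance for loss.

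**2. Bias formula.** Let p be the share of the intervention arm removed, R the mean days to GI-3 recovery of retained patients, and R + D the mean of removed patients. The mean of the arm as randomised is (1 − p)R + p(R + D) = R + pD. Analysing only retained patients therefore lowers the arm mean by **p × D**. The protocol gives neither p nor D; the values below are assumptions.

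**3. False-positive rate with no true effect.** SE = SD × √(1/64 + 1/(64(1 − p))). With b = pD, the rejection probability is Φ(b/SE − 1.96) + Φ(−b/SE − 1.96). Example: p = 10%, D = 2, SD = 1.0 gives SE = 0.182, b/SE = 1.10 and a probability of 19.6%.

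| p (patients of 64) | D, days | Bias, days | Share of 0.375 | Share of 0.5 | False-positive rate, SD 1.0 to 0.75 |
|---|---|---|---|---|---|
| any | 0 | 0 | 0% | 0% | 5% |
| 2% (1.3) | 1 | 0.02 | 5% | 4% | 5.1% to 5.3% |
| 5% (3.2) | 1 | 0.05 | 13% | 10% | 5.9% to 6.6% |
| 10% (6.4) | 1 | 0.10 | 27% | 20% | 8.5% to 11.4% |
| 10% (6.4) | 2 | 0.20 | 53% | 40% | 19.6% to 31.2% |

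With 1 to 3 removals and D up to 2 days, the bias is at most 3/64 × 2 = 0.09 day.

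**4. The schedule effect alone.** Assume a 5% chance of stopping at each exam, unrelated to bowel function, and one exam per day up to recovery. Assume recovery on days 1 to 5 in shares of 68, 20, 7, 3 and 2%, a mean of 1.51 days. The chance of removal for recovery on day k is 1 − 0.95^k. Then 7.4% of the arm is removed, with a mean of 2.01 days. Retained patients average (1.51 − 0.148)/(1 − 0.074) = 1.47 days, where 0.148 is the removed patients' contribution to the mean. The arm mean falls by 0.04 day with no true effect. This part is modest. It would also change if later exams are fewer than daily, since the table in Part A, item 5 lists exams on days 2 to 5 only if criteria are met.

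**5. Lost numbers.** At d = 0.5, losing 2%, 5% or 10% of one arm lowers power from 80.1% to 79.7%, 79.1% or 78.0%. The issue is bias, not power.

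**The case against.** **The rule may rarely operate.** Part D calls the discomfort mild, and it could come from the incision rather than from a slow bowel. This stands as a limit on size: with few removals, or no difference in recovery, the bias is negligible or zero.

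**The sentences are assurances to patients in a risk section, and the analysis set may be settled in an analysis plan not shown.** This stands in part. A reader might infer that the comparison is biased as designed. The protocol does not support that: bias also needs removed patients to differ in outcome and their data to be left out. But who stays in follow-up is a matter for the protocol, and its words are removal from the study.

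**The data may not be lost.** A reader might infer that no analysis could repair the loss. Outcomes come from the hospital record, so they may still exist there. Whether they may be used depends on consent wording, which is not available here. An analysis plan could not use outcomes that were never abstracted, but the loss is not shown to be beyond recovery.

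**The sentence about data from both groups suggests that controls are scanned too.** This does not defeat the one-arm reading, because the Brief Summary is explicit and no control exam is scheduled. The two places should be reconciled.

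**Conclusion.** The point holds in conditional form. Followed as written, the rule permits loss after randomisation in the intervention arm only. If removed patients recover more slowly and are left out of the analysis, the result is shifted in favour of G-POCUS. The repeated exams give slow recoverers more chances to be removed, so some link with outcome can arise from the design itself.

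The size cannot be known from the protocol. Under the assumed values it runs from zero to 0.20 day, or up to 53% of a 0.375-day target and 40% of a 0.5-day target. The upper end needs 10% removed and a 2-day difference, neither of which the protocol supports or excludes. The rule is worth changing because the general right to discontinue already protects patients and follow-up by chart needs no further exam.

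**What to change.** In Part D, items 2 and 6, replace removal from the study with wording such as: *A patient who asks to stop has no further ultrasound exams but stays in the study. Outcomes continue to be collected by chart review, and the patient is analysed in the arm to which they were randomised. A patient is removed only on withdrawing consent to the use of their data. The reason for stopping is recorded.* Care after the exams stop is for the investigators to state.

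Reconcile the sentence in Part A, item 4b about data from both groups with the Brief Summary, so that it is clear whether any control patient is scanned.

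With this change p = 0 for this rule, so the bias from it disappears and all 64 + 64 patients can be analysed.

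The cost is two sentences, matching consent wording and slight dilution. If 5% stop the exams and gain nothing from the intervention, a 0.375-day effect becomes 0.95 × 0.375 = 0.356 day; at 10% it becomes 0.338 day. No new procedure is needed.
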